The main outcome of our study will be incidence of dose reduction/interruption, calculated separately for pirfenidone and nintedanib. For each patient, average daily dose will be calculated in pre-specified time-periods (for example – the first 6 months, the first 12 months, and the average daily dose calculated separately in each month since drug initiation) (more details in section 2.6). Incidence of dose reduction/interruption will be defined as average daily dose not following the prescribing information (PI). According to the PI, the daily dose of pirfenidone is 2403 mg [13], hence the study will consider average daily dose less than 2165 mg (90% of PI dose) as dose reduction for pirfenidone [12]. For nintedanib, the daily dose allowed under prescriber information is 200 mg [14], hence less than 200 mg will be considered a dose reduction for nintedanib patients. As a secondary outcome, we will also assess drug discontinuation during first 6 and 12 months separately for pirfenidone and nintedanib and will be defined as a gap of at least 60 days in filling of prescription (a gap of 60 days after the prescription date + days of supply for the current prescription). In a sensitivity analysis, we will explore 30- and 90- days gap as a definition for drug discontinuation. As this is a descriptive study, assessment of the dose reduction and discontinuation for both drugs will be considered separately, and only descriptively, without any direct comparison between the two cohorts.

NIS Protocol Page 16 of 36

Study number: 1199-0526 Document number: c41847952-01

Proprietary confidential information © 2023 Boehringer Ingelheim International GmbH or one or more of its affiliated companies

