9.3.2 Outcomes

9.3.2.1 Primary outcome

The main outcome measure of our study is the incidence of dose reduction/interruption, calculated separately for each drug. For calculating the primary outcome, we will first need to calculate the average daily dose of pirfenidone and nintedanib after drug initiation (post-index period). Specific details of calculations are —

Average daily dose

Average daily dose for each patient will be calculated by taking the average of total drug intake (tablet strength * number of doses) during the time between index date to the date of drug discontinuation

```
Average \ Daily \ Dose \\ = \frac{\sum_{0}^{n}(Tablet \ Strength*number \ of \ tablets \ in \ a \ Rx \ fill)}{Time \ of \ follow - up \{(Date \ of \ discontinuation) - Index \ Date\}} Where n = number of fills a patient has received for pirfenidone/nintedanib
```

- We will calculate average daily dose of pirfenidone and nintedanib separately for each month in post-index period (month 1 to 12) and will also calculate for cumulative periods of 6 months and 12 months. For all calculations, censoring events will be taken into account, with patient censored at the date of drug discontinuation, or end of 12 months.
- Six and twelve months average daily dose categories For the average daily dose calculations in cumulative periods, we will be dividing the patients in following 4 categories
 - 1) Dose strength less than 50%
 - 2) Dose strength between 51% to 66%
 - 3) Dose strength between 67% to 90%
 - 4) Dose strength above 90%

Incidence of Dose Reduction and/or temporary dose interruption

Once average daily dose is calculated for each month post-index (month 1 to 12), incidence of dose reduction/interruption will be calculated as presence of average daily dose $\leq 90\%$ dose strength (for pirfenidone) or $\leq 66.67\%$ dose strength (for nintedanib), as per the PI [12 – 14]. Patients will be required to have the dose reduction for at least for 60 days, to make sure that the dose reduction is not temporary.

In a sensitivity analysis, we will also evaluate temporary dose reductions, i.e., dose reduced to below the above defined dose strength only for 1 month.

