In the primary analysis, patients who reduce their dose in the prior months will be allowed to discontinue the drug in future months (For example, in primary analysis, a patient can reduce their index drug dose in month 2 (i.e. dose below label recommendation for the whole month 2 and 3), and then can discontinue the drug in month 4 (or beyond). We will also evaluate the incidence of dose reduction in patients who never discontinue the index drug.

NIS Protocol Page 19 of 36

Study number: 1199-0526 Document number: c41847952-01

Proprietary confidential information © 2023 Boehringer Ingelheim International GmbH or one or more of its affiliated companies

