9.7 DATA ANALYSIS

9.7.1 Main analysis

Baseline characteristics for the pirfenidone and nintedanib cohorts will be reported as frequencies with percentages for categorical data, and means with standard deviations (SD), and median with interquartile range will be reported for continuous variables. We will compare the baseline characteristics using Student's T-test or Wilcoxon rank-sum test for continuous variable, and chi-square test for categorical variable

Average daily dose during first 6 months and 12 months after drug initiation will be reported as means with standard deviations (SD), and median with interquartile range. Six months and 12-months daily dose categories will be presented as frequencies with percentages. Incidence of dose reduction will be reported by month of occurrence (using month 2 and onwards) and reported as frequencies with percentages. Time to drug dose reduction will be reported in months (mean (SD)). Drug discontinuation will be reported as frequencies with percentages, and time to drug discontinuation will be reported in months (mean (SD)). As this is a descriptive study, there will be no multivariable adjustment and/or direct comparison of outcomes between the pirfenidone and nintedanib cohort.

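### The primary outcome tests a dose level, not a fall in dose, so patients who are low from the start are most naturally counted as month-2 reductions and shorten the mean time to reduction

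*Combined protocol and SAP*

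**What the plan says.** Section 9.1 frames the outcome as a level: "Incidence of dose reduction/interruption will be defined as average daily dose not following the prescribing information (PI"). For pirfenidone it continues, "hence the study will consider average daily dose less than 2165 mg (90% of PI dose) as dose reduction for pirfenidone"; for nintedanib, "hence less than 200 mg will be considered a dose reduction for nintedanib patients".

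Section 9.3.2.1 makes this operational. After a dose is calculated for each of months 1 to 12, "incidence of dose reduction/interruption will be calculated as presence of average daily dose" at or below 90% of full dose (pirfenidone) or 66.67% (nintedanib). It adds a duration condition: "Patients will be required to have the dose reduction for at least for 60 days". Its worked example is that "a patient can reduce their index drug dose in month 2 (i.e. dose below label recommendation for the whole month 2 and 3"); the example is silent on month 1.

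Section 9.7.1 then says: "Incidence of dose reduction will be reported by month of occurrence (using month 2 and onwards"), and "Time to drug dose reduction will be reported in months (mean (SD")).

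No section requires an earlier month above the cut-off, removes patients already low from the group at risk, or reports them separately. The sensitivity analysis in Section 9.3.2.1 changes only the duration (one month). The further analysis there restricts to patients who never discontinue, which leaves constantly low patients in.

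**The concern.** An incident reduction, and above all a time to reduction, presupposes a higher dose from which the patient came down. Under the written rule, a patient who starts at or below the cut-off and stays there meets the event definition without any fall. So does a patient who is low through month 3 and then rises above the cut-off, although that dose only went up. The 60-day condition does not screen out either patient; both meet it automatically by remaining on drug.

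The overarching aim in Section 8 is the incidence of dose reduction and discontinuation, and Section 7 expects the results to inform decision makers. A reader of a table headed dose reduction will take it to mean patients who came down. As written, the table mixes them with patients who were never above the cut-off, and the mean time takes in patients for whom no such time exists, each at the earliest reportable month. Section 9.7.2 may carry the same outcome into matched cohorts.

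**Working it through.** The protocol gives no expected incidence, time to reduction or share of patients below the cut-off, so there is no planned figure to reproduce. The check has two parts.

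**1. The rule applied to constructed dose histories.** Protocol inputs: the cut-offs in Sections 9.3.2.1 and 9.1; 60 days read as two consecutive months, as in the protocol's example; first reportable month 2. The histories are illustrations.

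| History (mg/day) | 9.3.2.1 rule | 9.1 rule | Earlier month above cut-off required |
|---|---|---|---|
| Pirfenidone 1602, all 12 months | month 2 | month 2 | no event |
| Nintedanib 150, all 12 months | month 2 | month 2 | no event |
| Nintedanib 200, all 12 months | month 2 | no event | no event |
| Pirfenidone 2403 in month 1, then 1602 | month 2 | month 2 | month 2 |
| Pirfenidone 2403 to month 5, then 1602 | month 6 | month 6 | month 6 |
| Nintedanib 300 to month 5, then 150 | month 6 | month 6 | month 6 |
| Pirfenidone 1602, stops after 2 months | no event | no event | no event |

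The prior-dose condition removes only the flat-low histories. Genuine falls keep their month, including a fall in month 2, provided month 1 counts as an earlier month.

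The third row shows a conflict in the text: 200/300 = 66.667%, which is at or below 66.67% (Section 9.3.2.1), but 200 is not less than 200 (Sections 7 and 9.1). For pirfenidone the two forms nearly agree: 0.90 × 2403 = 2162.7 mg, against 2165 mg.

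**2. Size under assumptions.** Among patients on drug long enough to be counted, let f be the share never above the cut-off, p the share of the others who later reduce, and m the mean onset month of those reductions. None of the three is in the protocol.

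- Combined figure as written: f + (1 − f)p
- True falls among all such patients: (1 − f)p
- True falls among those ever above: p
- Mean time as written: [2f + (1 − f)p·m] / [f + (1 − f)p]

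With p = 30% and m = 6:

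- f = 10%: combined 10 + 0.9 × 30 = 37%; falls 27% of all, 30% of those ever above; mean time (10 × 2 + 27 × 6)/37 = 4.9 months.
- f = 20%: combined 20 + 0.8 × 30 = 44%; falls 24% of all, 30% of those ever above; mean time (20 × 2 + 24 × 6)/44 = 4.2 months.

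A wider range, still with m = 6:

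| f | p | Combined | Falls, of all | Falls, of ever above | Mean time as written (months) |
|---|---|---|---|---|---|
| 5% | 20% | 24% | 19% | 20% | 5.2 |
| 10% | 20% | 28% | 18% | 20% | 4.6 |
| 20% | 20% | 36% | 16% | 20% | 3.8 |
| 30% | 20% | 44% | 14% | 20% | 3.3 |
| 5% | 40% | 43% | 38% | 40% | 5.5 |
| 10% | 40% | 46% | 36% | 40% | 5.1 |
| 20% | 40% | 52% | 32% | 40% | 4.5 |
| 30% | 40% | 58% | 28% | 40% | 3.9 |

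The shortening of the mean is (m − 2) × f / [f + (1 − f)p], so it grows in proportion to m − 2. For f = 10%, p = 30%, m = 6 it is 4 × 10/37 = 1.1 months. The direction needs no assumed values: the mean falls whenever f > 0 and m > 2.

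**The case against.** The strongest reply is that Sections 7 and 9.1 define the outcome as dosing that does not follow the label, and that Section 7 gives possible sub-optimal dosing as the motive. For that outcome a patient always below the cut-off is a true positive. This stands. A reader might infer that the reported incidence is simply inflated, but the documents do not support that: the excess exists only against a definition requiring a fall from a dose once reached, which the protocol does not adopt.

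Second, the text does not settle the handling of month 1. Reporting from month 2 could mean that patients already low are set aside, and the language of reducing a dose can imply a higher start. This stands in part. Nothing says such patients are dropped, and the worked example defines a month-2 event solely by low doses in months 2 and 3, so counting them is the more natural reading but not a stated rule.

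Third, the size is assumed. One never-above share need not fit both drugs, whose cut-offs differ; patients who stop before completing 60 low days are not counted; and setting 37% against 30% would compare different denominators. All of this is right, which is why the working is limited to patients treated long enough to be counted and shows both denominators.

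Fourth, incidence by month would reveal a cluster in month 2. It would, but it could not separate patients low from the start from those who truly fell in month 2, and the mean time would remain blended.

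**Conclusion.** The outcome is sound as a measure of sub-label dosing but does not measure incident reduction, and the mean time to dose reduction is wrong in meaning for any patient who had no fall. With 10% or 20% never above the cut-off, 30% of the rest reducing and a mean onset of month 6, the combined figure is 37% or 44%, against falls in 27% or 24% of the same patients (30% of those ever above), and the mean time is 4.9 or 4.2 months against 6. These values rest wholly on assumptions and on the reading that patients low in month 1 are carried into month 2; if the never-above share is near zero, so is the effect.

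A reader might also infer that the contrast between the two drugs is distorted. The documents do not support that: the main analysis plans no direct comparison of outcomes, and nothing shows how the never-above share differs by drug. The point is worth settling before the analysis because this is the main outcome of a descriptive study.

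**What to change.** - Keep the combined figure and label it as sub-label dosing.
- Split it, by drug, into reduction after at least one earlier month above the cut-off, and low dosing with no earlier month above the cut-off. State how a patient with both patterns is classified.
- Compute time to reduction in the first group only.
- State the denominator of each percentage, and whether month 1 counts as an earlier month.
- State how fills are allocated to months. If a fill counts wholly in the month it is dispensed, two fills in one month would put a patient at 67% of full dose at about 134%, creating a false month above the cut-off.
- Reconcile the nintedanib cut-off in Section 9.3.2.1 (at or below 66.67%) with Sections 7 and 9.1 (below 200 mg), since this decides whether patients constantly at 200 mg/day are counted.

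The cost is one derived flag and a few table rows, from monthly doses that the protocol already calculates. The downsides are a lower headline reduction figure and some misclassification of the flag, because the doses come from fills, which Section 9.9 acknowledges may not reflect actual intake.

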Variables:	The main outcome of our study will be incidence of dose reduction/interruption, calculated separately for nintedanib and pirfenidone. For each patient, average daily dose will be calculated in pre-specified time-periods (for example – the first 6 months, the first 12 months, and the average daily dose calculated separately in each month since drug initiation). Incidence of dose reduction/interruption will be defined as average daily dose not following the prescribing information.		
	As a secondary outcome, we will also assess drug discontinuation during first 6 and 12 months separately for pirfenidone and nintedanib and will be defined as a gap of at least 60 days in filling of prescription (a gap of 60 days after the prescription date + days of supply for the current prescription).		
Data sources:	We will use administrative health insurance claims data from the Optum Research Database (ORD) for the period of October 1, 2013 through end of data availability (currently September 30, 2022). This database was chosen as it includes claims of Medicare Advantage and commercially enrolled beneficiaries.		
Study size:	As this is a descriptive study, no formal calculation of sample size was performed. In a preliminary feasibility analysis using Optum data to examine sample size, we have found that 1,979 patients newly		

NIS Protocol Page 9 of 36

Name of company:			
Boehringer Ingelheim			
Name of finished medicinal product: Nintedanib (Ofev) and Pirfenidone (Esbriet)			
Name of active ing Nintedanib (Ofev) : Pirfenidone (Esbrie	and		
Protocol date:	Study number:	Version/Revision:	Version/Revision date:
24 MAR 2023	1199-0526		
	initiated pirfenidone, and 2,559 patients who initiated nintedanib between 10/2014 to 12/2020. As such, this study is expected to have a sufficient sample.		

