7. RATIONALE AND BACKGROUND

Idiopathic pulmonary fibrosis (IPF) is a life-threatening rare disease characterized by decline in lung function due to progression of fibrosis in the interstitium of the lung [1]. In patients with IPF, a decline in forced vital capacity (FVC) is an important indicator of mortality [6]. The median survival of non-treated IPF patients is approximately 3 years from diagnosis [2].

[figure not shown]
Before anti-fibrotic medications became available in the US, IPF treatment mainly consisted of therapeutics that were found not to be of benefit (or even harmful), and a mainstay of care focused on symptom relief and included palliative care [3]. In October 2014, two anti-fibrotic medications, nintedanib and pirfenidone, were approved by the U.S. Food and Drug Administration (FDA) for the treatment of IPF [4, 5], which transformed the treatment of this disease. Both medications were found to reduce the rate of decline in FVC compared to placebo in phase III clinical trials [7, 8].

From the perspective of treatment, the approvals of antifibrotics for IPF were significant breakthroughs. Antifibrotics have demonstrated an ability to slow IPF progression, if taken according to the recommended dosing in the prescriber information and taken continuously, in both clinical trials [7, 8] and real-world evidence [9]. Previous real-world studies have compared persistence/ discontinuation patterns for pirfenidone and nintedanib and found similar persistence patterns for both drugs [10, 11]. However, these studies have failed to consider the differential dosing regimens between these two drugs and corresponding incidence of dose reduction and/or temporary dose interruption. Hence, this study will assess both dose reduction and/or temporary dose interruption and discontinuation patterns for pirfenidone and nintedanib among patients with IPF.

In this study, we will investigate the incidence of dose reduction/interruption beyond the label recommendations (defined as a dose not following the prescriber information (PI), which corresponds to a daily dose of 2165 mg (90% of full dose, which is 2403 mg) for pirfenidone [12, 13] or less than a daily dose of 200 mg for nintedanib (66.67% of full dose, which is 300 mg) [14]) from 10/01/2014 to 09/30/2022 using real-world data. The definition of incidence of dose reduction, which is differential for nintedanib and pirfenidone is because of –

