- 1) In the US, the prescriber information (PI) and/or label for pirfenidone does not indicate any particular dose reduction recommended as per Food & Drug Administration (FDA). For nintedanib, reducing dose from 150 mg to 100 mg BID is part of the PI.
- 2) The post-hoc analysis of clinical trials showed similar slope of FVC decline for patients who reduced the dose to 100 mg BID for nintedanib, but for pirfenidone, the slope of FVC decline was steeper for patients who reduced the dose, potentially indicating that reduced dose might lead to lower benefit on FVC decline (see figures below) [12, 15]

Proprietary confidential information © 2023 Boehringer Ingelheim International GmbH or one or more of its affiliated companies

The current study may be able to demonstrate to decision makers the differential complexities in dosing regimen for pirfenidone vs. nintedanib and may reveal that IPF patients may not be receiving the full benefit of pirfenidone due to possible sub-optimal dosing, even when the patient has not discontinued the drug.

NIS Protocol Page 14 of 36

Study number: 1199-0526 Document number: c41847952-01

Proprietary confidential information © 2023 Boehringer Ingelheim International GmbH or one or more of its affiliated companies

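### The main-outcome rule in Section 9.3.2.1 counts nintedanib at exactly 200 mg/day as a dose reduction; Sections 7 and 9.1 count only doses below 200 mg/day and treat 200 mg/day as within the label

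*Combined protocol and SAP*

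**What the plan says.** Section 9.3.2.1, which defines the main outcome, counts a nintedanib dose reduction or interruption when the monthly average daily dose is "\leq 66.67\%$ dose strength (for nintedanib), as per the PI" (the code at the start is the less-than-or-equal sign). The reduction must last at least 60 days.

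The other sections put the boundary on the other side of 200 mg/day:

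- Section 7 describes the event as "less than a daily dose of 200 mg for nintedanib (66.67% of full dose, which is 300 mg".
- Section 9.1 states that "the daily dose allowed under prescriber information is 200 mg" and then "hence less than 200 mg will be considered a dose reduction for nintedanib patients".
- Section 7 explains why the two drugs have different cut-offs: "For nintedanib, reducing dose from 150 mg to 100 mg BID is part of the PI".
- The Abstract gives the concept behind the outcome: "Incidence of dose reduction/interruption will be defined as average daily dose not following the prescribing information". Section 9.1 repeats it.
- Within Section 9.3.2.1, the one-month sensitivity analysis speaks of "dose reduced to below the above defined dose strength only for 1 month", and the worked example of a reduction followed by discontinuation speaks of "dose below label recommendation for the whole month 2 and 3".

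Nothing in the protocol reconciles the inclusive rule with the strict one.

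**The concern.** The disputed boundary is the total daily dose of the one reduced regimen that the protocol names as within the label, 100 mg twice daily. The sign therefore decides how a patient averaging exactly that dose is classified. Under the rule in Section 9.3.2.1, two consecutive months at exactly 200 mg/day are an event. Under Sections 7 and 9.1 they are not.

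Section 9.3.2.1 is the text a programmer would code from. An error there would carry into monthly incidence and mean time to dose reduction (Section 9.7.1), the subset who never discontinue (Section 9.3.2.1), and any re-analysis in matched cohorts (Section 9.7.2). It would also undercut the argument in Section 7 for drug-specific cut-offs, which rests on 100 mg twice daily being a labelled nintedanib dose.

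**Working it through.** **Inputs.** Full nintedanib dose 300 mg/day and cut-off 200 mg/day (Section 7); inclusive cut-off 66.67% (Section 9.3.2.1); typical supply 30 days per fill (Section 9.3.2.2); 100 mg twice daily, so 60 capsules of 100 mg, or 6,000 mg, per 30-day fill.

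**1. The protocol's own figure.** 200/300 = 66.667%, which rounds to the stated 66.67%.

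**2. Exactly 200 mg/day under each rule.**

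- Section 9.3.2.1: 66.667% ≤ 66.67% is true, so it is an event. In mg, 0.6667 × 300 = 200.01 mg/day.
- Sections 7 and 9.1: 200 < 200 is false, so it is not an event.

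The rules disagree from 200.00 to 200.01 mg/day and nowhere else.

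**3. Rounding.** Replacing ≤ with < while keeping 66.67% would not remove the conflict, because 66.667% is also strictly below 66.67%.

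**4. When does an average of exactly 200 arise?** Average = mg dispensed ÷ days.

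| Supply | Days | Average (mg/day) | Section 9.3.2.1 | Sections 7 and 9.1 |
|---|---|---|---|---|
| One fill, 6,000 mg | 29 | 206.9 | no event | no event |
| One fill, 6,000 mg | 30 | 200.0 | **event** | **no event** |
| One fill, 6,000 mg | 365/12 | 197.3 | event | event |
| One fill, 6,000 mg | 31 | 193.5 | event | event |
| Two fills, 12,000 mg | 59 | 203.4 | no event | no event |
| Two fills, 12,000 mg | 60 | 200.0 | **event** | **no event** |
| Two fills, 12,000 mg | 61 | 196.7 | event | event |

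With n fills exactly on schedule, n × 6,000 ÷ (n × 30) = 200.0 for any n. Two such 30-day months satisfy the 60-day requirement.

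**5. Dependence on unstated choices.** The protocol gives neither the month length nor the way fills are assigned to months. If averages use raw fill timing, one day's shift over two fills brings the rules into agreement. If instead each fill is spread over its days of supply (an assumption), every fully covered month on 100 mg twice daily averages exactly 200 mg/day, whatever the month's length. The sign would then decide the classification of every patient continuously on that regimen.

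**The case against.** The strongest reply is that this is a one-symbol slip with an evident reading. Sections 7 and 9.1, the Abstract's concept, the sensitivity analysis and the worked example all point to the strict rule, and even the disputed sentence appeals to the label. The text reviewed was read from PDF by a program, so the sign could be a reading error; it appears for both drugs in that sentence, which fits either explanation. The practical effect may also be nil: a day's variation in refill timing is enough for the rules to agree, and a patient followed for 365 days with 12 or 13 fills averages 72,000/365 = 197.3 or 78,000/365 = 213.7 mg/day, neither of which is 200.

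Much of this stands. The sign must be checked in the source file, the size is unknown, and incidence may not move at all. The 365-day example concerns the cumulative average, however, whereas the event is defined on monthly averages, where exactly 200 can occur. Clear intent elsewhere does not protect a programmer who works from Section 9.3.2.1 alone. As supplied, the text tells two programmers using different sections to classify the same patient in opposite ways.

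**Conclusion.** The concern holds. As printed, the main-outcome rule counts exactly 200 mg/day of nintedanib as an event, against Sections 7 and 9.1 and against the protocol's own concept of the outcome. The inclusive sign in Section 9.3.2.1 is the outlier. Relative to the strict rule it can only raise nintedanib incidence or leave it unchanged.

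The amount cannot be quantified from the documents. It depends on how many patients take 100 mg twice daily, how regularly they refill, the month length, and how fills are assigned to months. It could range from no effect to reclassifying every patient steadily on that regimen who has no other qualifying reduction. The conclusion assumes the sign in the source file matches the text reviewed. This should be fixed before coding.

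**What to change.** Check the sign in the source file. Then reconcile Sections 7, 9.1 and 9.3.2.1 to one nintedanib event rule with one operator, consistent with the outcome concept in the Abstract and Section 9.1. State it in mg/day, because the rounded percentage recreates the problem under either sign. State the month length and how fills are allocated to months. The operator alone does not settle late refills: 60 capsules over 31 days average 193.5 mg/day, an event under both rules.

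Two smaller points can be tidied in the same edit:

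- **Pirfenidone cut-off.** 0.90 × 2,403 = 2,162.7 mg, whereas 2,165 mg is 90.1%, a difference of 2.3 mg. Section 9.1 uses a strict operator and Section 9.3.2.1 an inclusive one. Use one value and one operator.
- **Cumulative dose categories.** Make them contiguous. Exactly 50% falls in none, and 66.67% falls in none unless rounded to a whole number.

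The cost is protocol wording and one line of code. The change concerns outcome cut-points only and implies no view on dosing.

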9.3.2.2 Secondary outcomes

We will assess drug discontinuation as a secondary outcome. Pirfenidone or nintedanib discontinuation will be defined as presence of sixty or more days gap in refilling a prescription of the drug (sixty days gap counted from the date of last fill plus the days of supply for the fill). The date of last fill plus the days of supply for the fill (typically 30 days) will be designated as date of discontinuation, and time to discontinuation will be calculated as time between date of discontinuation and index date (only for patients who discontinue the drug). We will calculate the percentage of patients who discontinue each drug in first 6- and 12-months post-index period. As a sensitivity analysis, we will calculate drug discontinuation using 30 days and 90 days as allowed gap between the scripts (vs. 60 days)

We will also assess how many patients initiate either of the antifibrotic drugs (including the same drug the patient has discontinued) during the follow-up time post discontinuation of their index drug. We will separately assess initiation of the index drug vs. initiation of the other antifibrotic agent.

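### A full interruption of 60 days or more is censored on its first day, so it cannot itself count in the primary dose reduction/interruption outcome, even when the same drug is later refilled

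*Combined protocol and SAP*

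**What the plan says.** The primary outcome in section 9.3.2.1 is the incidence of dose reduction and/or temporary interruption. It is judged from monthly average daily dose against a cut-off of 90% of full dose for pirfenidone and 66.67% for nintedanib. The duration rule is: "Patients will be required to have the dose reduction for at least for 60 days, to make sure that the dose reduction is not temporary". The worked example in the same section describes a patient with the "dose below label recommendation for the whole month 2 and 3".

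For all dose calculations, "censoring events will be taken into account, with patient censored at the date of drug discontinuation, or end of 12 months". The average-dose formula also ends its denominator at discontinuation. No rule returns a patient to follow-up after a refill.

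Section 9.3.2.2 defines discontinuation as "presence of sixty or more days gap in refilling a prescription of the drug". The date is set back to the end of the last supply: "The date of last fill plus the days of supply for the fill (typically 30 days) will be designated as date of discontinuation". That is the first day of the gap. The same section plans a separate count of patients who "initiate either of the antifibrotic drugs (including the same drug the patient has discontinued) during the follow-up time" after stopping, with index-drug restarts split from switches.

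**The concern.** The two 60-day rules meet at the same number and work against each other. The outcome needs at least 60 days of reduction. A complete pause shorter than that does not itself last long enough, and a complete pause that does last long enough is reclassified as discontinuation and removed from its first day. The removal applies even where the data show that the patient went back to the same drug.

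This bears on the main result. The primary aim (section 8) covers interruption, and section 7 faults earlier studies for overlooking temporary interruption. If the longest proven interruptions cannot enter the outcome, a reader of the reported incidence should be told so and should be able to see how far the figure depends on the censoring rule.

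**Working it through.** The plan is descriptive and has no event or sample-size calculation to reproduce (section 9.5). The check applies its rules to simple patients.

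**Inputs from the plan.** Cut-offs at or below 90% and 66.67%, reduction of at least 60 days, and censoring at discontinuation (9.3.2.1); a 60-day gap dated to the end of supply (9.3.2.2); events from month 2 onwards (9.7.1).

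**Assumptions.** 30-day months and a 360-day window; full dose apart from one complete pause; pause starting on any of days 30 to 359 (330 start days).

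**One patient.** Supply ends on day 90 and the next fill is on day 165.
- Gap = 165 − 90 = 75 days, which is at least 60, so discontinuation is dated to day 90.
- Average dose under the plan = 90/90 = 100% of full dose. No month is low, there is no primary event, and fills from day 165 on are not used.
- If the patient stays in follow-up and refills to day 360, the 12-month average is (360 − 75)/360 = 285/360 = 79.2%. Months 4 and 5 (days 90–149) have zero dose.

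**All start days.** The plan does not say how a fill is assigned to months, or whether 60 days means two monthly averages or 60 counted days. Three readings were tried:
- A: supply spread over the days it covers; event = two consecutive low months.
- B: dose credited to the month of the fill, with aligned 30-day fills (11 possible starts); event = two consecutive low months.
- C: a literal count of 60 consecutive reduced days.

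| Full pause | A, pirfenidone | A, nintedanib | B, either drug | C, either drug |
|---|---|---|---|---|
| 30 days | 250/330 | 110/330 | 0/11 | 0/330 |
| 45 days | 298/330 | 255/330 | 0/11 | 0/330 |
| 59 days | 298/330 | 291/330 | 0/11 | 0/330 |
| 60, 61, 75 or 90 days | 0/330 | 0/330 | 0/11 | 0/330 |

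**Reading the 59-day row.** Under A, all 272 start days that place the pause wholly within the 12 months give an event. The misses are late starts (from day 328 for pirfenidone, day 321 for nintedanib), where two low months no longer fit. Under B, the refill falls on the last day of the second gap month and restores that month to 100%, so only one month is low. Under C, 59 is less than 60.

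**Short pauses under A.** A 30-day month is low for pirfenidone with 3 missing days (27/30 = 90%) and for nintedanib with 10 (20/30 = 66.67%). A pause across a month boundary can therefore make two low months with 3 + 3 = 6 days or 10 + 10 = 20 days.

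**If a closed gap does not censor.** Among starts whose refill falls inside 12 months, a 60-day pause is an event in 270/270 (A), 9/9 (B) and 270/270 (C). A 90-day pause is an event in 240/240, 8/8 and 240/240. The results are the same for both drugs.

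**The case against.** The strongest reply is that this is a choice of definition. The duration rule is there to select sustained reduction while on drug, one-month reductions go to a sensitivity analysis, and a gap of 60 days or more is a separate state called discontinuation. Restarts are reported, so the information is not lost. In a descriptive study with no formal comparison of outcomes, that is a coherent scheme.

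Part of this stands. The 60-day definition is reasonable for the secondary outcome. Replacing the primary definition would also be debatable: it would classify a gap by a later refill, and 9.2.2 requires only 6 months of post-index enrolment for the 6-month analysis, so closure by month 12 could not be seen for everyone.

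It does not remove the point. The outcome is still labelled as covering interruption, and nothing else in the plan shows the effect of the censoring rule on it:
- The one-month sensitivity analysis uses the same censoring.
- The 30- and 90-day gap analyses are stated for discontinuation only.
- The analysis of patients who never discontinue removes these patients.
- The restart count returns nobody to the primary outcome.
- Section 9.9 says that reduction and interruption cannot be told apart; it does not say that long interruptions are excluded.

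A reader might go further and infer that a 59-day pause always counts while a 60-day pause never does. The first half holds only under reading A with the pause early enough in the window. A reader might also infer that these patients are treated as permanent stops throughout; in fact the plan reports their restarts separately.

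**Conclusion.** The point holds in this form: a complete gap of 60 days or more cannot itself count in the primary outcome, even when the same drug is refilled, and reductions after the restart are not counted either. This follows from the text and does not depend on which reading of the monthly rule is used. A patient with such a gap can still be an event through an earlier reduction, as the example in 9.3.2.1 allows. Whether a shorter full pause counts cannot be settled until the plan says how fills are assigned to months.

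It is tempting to conclude that the reported incidence is too low. The documents do not support that: under reading A, pauses as short as 6 days (pirfenidone) or 20 days (nintedanib) can also register as events, which pushes the other way, so the net direction is unknown. Nor can a share of affected patients be given. The documents contain no gap rate and no restart rate, and a product of assumed rates would include patients who already had an event before the gap.

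The enumeration rests on 30-day months and a single complete pause at otherwise full dose. It shows how the rules behave, not how often such pauses occur.

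**What to change.** In 9.3.2.1, add a sensitivity analysis of the primary outcome with these rules:
- A gap of 60 days or more that is closed by a fill of the same drug within the analysis window does not censor the patient. The window is 6 months for the 6-month cohort and 12 months for the 12-month cohort.
- Gap days count as zero dose, and later fills are used.
- The average-dose denominator runs to the first unclosed gap or the end of the window.

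Report it beside the primary result. Keep the 60-day gap definition for the secondary discontinuation outcome. State in 9.3.2.1 and 9.9 that the primary result excludes full interruptions of 60 days or more. Because the derivation cannot be programmed without a rule for assigning fills to months, write down the rule used.

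The cost is one extra derivation with its own follow-up end, from fill dates that the restart count already needs. The remaining weakness is that gaps late in the window have less time to close, so some interruptions will still be read as discontinuation. The report should say so.
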